10.0 EFFICACY ASSESSMENTS

The primary efficacy measurement is IOP at Hour 0, which will be measured in each eye using the Goldmann applanation tonometer. Two consecutive measurements will be taken for each eye. If the first 2 measurements differ by > 1 mm Hg, a third measurement will be taken. The IOP value for a given eye will be the median of all measurements, and this is consistent with the protocol IOP description in Study Protocol Section 6.1.1 (If the first 2 measurements differ by ≤ 1 mm Hg, the IOP for the given eye will be the average of the 2 readings. If the difference between the first 2 measurements is > 1 mm Hg, the IOP for the given eye will be the median of the 3 readings). For consenting patients at selected sites, additional IOP data will be collected at Hour 2 and 8, and these data will be included in diurnal IOP analyses.

Unless specified otherwise, the IOP measurements obtained after initiating the use of non-study IOP-lowering treatment (medications or procedures or both) in an eye will be excluded from the efficacy analysis.

10.1 PRIMARY EFFICACY ANALYSIS

The primary efficacy variable is Hour 0 IOP change from baseline (follow-up value minus baseline value, thus negative values reflect IOP reduction from baseline) assessed at Weeks 4, 12, and 24. Intraocular pressure values at Hour 0 at Baseline visit is considered as the baseline values.

Hour 0 IOP measurements at baseline, Weeks 4, 12 and 24 and changes from baseline will be descriptively summarized.

Primary efficacy analysis will be performed for patients treated with Bim SR 10 µg in the ITT population. The null and alternative hypotheses for the comparisons of IOP-lowering effect between Bim SR 10 µg and SLT at Weeks 4, 12, and 24 are:

- Null hypothesis: the difference in mean IOP change from baseline between the Bim SR 10 µg and SLT (Bim SR 10 µg minus SLT) is > 1.5 mmHg.
- Alternative hypothesis: the difference in mean IOP change from baseline between the Bim SR 10 µg and SLT (Bim SR 10 µg minus SLT) is ≤ 1.5 mmHg.

Hour 0 IOP change from baseline will be analyzed using a mixed effect model for repeated measurement (MMRM). The model will include Hour 0 IOP change from baseline as the response variable and treatment, visit, eye, baseline Hour 0 IOP, treatment-by-visit, visit-by-baseline Hour 0 IOP, visit-by-eye interactions as fixed effects. Unstructured covariance matrix for study visits and eyes will be used for repeated measures on the same patient. IOP measurements obtained after initiating the use of non-study IOP-lowering medication or procedure in an eye will be treated as missing. This will correspond to the hypothetical strategy defined in ICH E9 addendum (Section 18.0). If the model fails to converge, multiple imputation (MI) will be implemented for missing data before applying MMRM.

The mean difference in the Hour 0 IOP change from baseline between the Bim SR 10 µg and SLT (Bim SR 10 µg minus SLT) in the ITT population and the corresponding 95% confidence intervals (CI) will be constructed at each visit of Weeks 4, 12, and 24 from MMRM analysis. If the upper limit of the 95% CI is ≤ 1.5 mmHg at all 3 visits, the statistical noninferiority of Bim SR 10 µg to SLT is demonstrated.

For additional clinical consideration, Bim SR 10 µg is considered clinically noninferior to SLT if the upper limit of the 95% CI is ≤ 1.0 mmHg at 2 out of the 3 visits.

Sample SAS® code for primary analysis is shown as below:

```
proc mixed data=iop;
  where avisitn >1;
  class subjid eye trt avisitn;
  model chg=trt avisitn eye base trt*avisitn
        avisitn*base avisitn*eye/ddfm=kr;
```

```
repeated avisitn*eye/type=un subject=subjid rcorr;  
lsmeans trt*avisitn/diff;  
run;
```

The definitions of variables are:

chg = Hour 0 IOP change from baseline at the primary analysis time points of
Week 4, Week 12, and Week 24

avisitn = Derived analysis visits at Week 4, Week 12, and Week 24

subjid = Subject ID

eye = Variable to indicate primary eye or contralateral eye

trt = Variable to indicate Bim SR treatment or SLT treatment

base = Baseline IOP

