10.2 SECONDARY ANALYSIS

10.2.1 Superiority Test of Bim SR 10 µg versus SLT

As the secondary efficacy analysis, a superiority test of Bim SR 10 µg versus SLT will be performed if the statistical noninferiority is demonstrated in the primary efficacy analysis for the ITT population as the gatekeeping procedure to control overall type I error rate at the 0.05 level. Superiority of Bim SR 10 µg versus SLT is considered achieved if the upper limit of the 95% CI is < 0 mmHg at Weeks 4, 12, and 24.

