15.0 DETERMINATION OF SAMPLE SIZE

The sample size calculation is based on paired-eye differences using a normal approximation with a 2-sided significance level of 0.05, assuming that there is no difference in mean IOP change from baseline between Bim SR 10 µg eyes and SLT eyes, and that change from baseline in IOP has a standard deviation of 4 mmHg. A sample size of 144 patients with eyes treated with Bim SR 10 µg and SLT will provide approximately 98% power in showing noninferiority in 3 out of 3 timepoints with a noninferiority margin of 1.5 mm Hg, and 90% power in showing noninferiority in 2 out of 3 timepoints with a noninferiority margin of 1.0 mmHg, assuming that both the between-eyes and the within-patient correlation coefficients are 0.5.

Assuming a premature discontinuation rate of 10%, approximately 160 patients are to be enrolled into this study and treated with Bim SR 10 µg. Additionally, there are 55 Bim SR 15 µg treated patients who were enrolled before implementation of Amendment 3 and treated with the 15 µg Bim SR dose strength.

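### As written, the 2-of-3 clinical noninferiority conclusion does not require statistical noninferiority first, so it can stand beside a failed primary analysis

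*SAP*

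**What the plan says.** SAP 10.1 contains two pass/fail rules, both read from the 95% confidence intervals at Weeks 4, 12 and 24. Statistical noninferiority needs an upper limit of at most 1.5 mm Hg at all three visits. A separate sentence, labelled as an additional clinical consideration, says that the product "is considered clinically noninferior to SLT if the upper limit of the 95% CI is" at most 1.0 mm Hg at 2 of the 3 visits. Protocol 7.3.1 and the protocol summary give the same second rule, joined to the first by a simple *in addition*. No text says which two visits must pass, limits the third visit, or makes the second rule depend on the first.

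Superiority is treated differently. SAP 10.2.1 allows that test only after statistical noninferiority, "as the gatekeeping procedure to control overall type I error rate at the 0.05 level". Protocol 7.3.2 has the same order.

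The sample-size sections (SAP 15.0, Protocol 7.5) state power for both rules: about 98% for the first and "90% power in showing noninferiority in 2 out of 3 timepoints" at the 1.0 mm Hg margin for the second. They give no joint power.

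**The concern.** The second rule has its own margin, its own threshold and a named conclusion. It sits in the primary analysis section, and the trial reports power for it. Followed literally, it can be met at Weeks 4 and 12 while Week 24 fails the 1.5 mm Hg limit. The report could then say both that statistical noninferiority was not shown and that the product is clinically noninferior.

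Week 24 is the visit where a split is most plausible. Protocol 1.2 expects the implant to release drug over about 4 months. Since Amendment 6 the second administration depends on retreatment criteria, and it may come after Week 16 or not at all (Protocol 5.9.1.5). SAP 10.4.5 already plans a sensitivity analysis of how second-administration timing affects Week 24. A 2-of-3 rule with no condition attached lets exactly that visit be set aside.

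**Working it through.** **Inputs (SAP 15.0).**
- Test: "normal approximation with a 2-sided significance level of 0.05", so each upper limit is the estimate plus 1.96 standard errors.
- Variability: "change from baseline in IOP has a standard deviation of 4 mmHg", per eye.
- Correlation: "assuming that both the between-eyes and the within-patient correlation coefficients are 0.5". The second coefficient is taken here as the correlation of the paired differences between visits.
- Size: 144 patients.
- Truth used for the plan's power: "assuming that there is no difference in mean IOP change from baseline between" the two eyes.

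**Reproducing the plan's figures.**
- SD of the paired difference = √(4² + 4² − 2 × 0.5 × 4 × 4) = 4.0. SE = 4/√144 = 0.333. 1.96 × SE = 0.653.
- Power at one visit = Φ(margin/SE − 1.96). Margin 1.5: Φ(4.5 − 1.96) = 99.4%. Margin 1.0: Φ(3.0 − 1.96) = 85.1%.
- Joint over three visits (trivariate normal, correlation 0.5, 4 million draws): 98.5% for 3 of 3 at 1.5, and 88.9% for at least 2 of 3 at 1.0. The plan states about 98% and 90%, so both are reproduced.
- Reading the rule as exactly 2 of 3 gives 19.6%, so the stated 90% must mean at least 2. Independent visits give 94.0% for the second figure and correlation 0.75 gives 86.8%; neither fits as well.

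**When the two rules disagree.** A visit passes 1.5 if its estimate is at most 1.5 − 0.653 = 0.847, and passes 1.0 if its estimate is at most 1.0 − 0.653 = 0.347. The documents give no expected difference by visit, so the patterns below are assumptions.

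| True difference, Weeks 4 / 12 / 24 (mm Hg) | Statistical rule met | Clinical rule met | Clinical met, statistical failed | Clinical met if gated |
|---|---|---|---|---|
| 0 / 0 / 0 | 98.5% | 88.9% | 0.3% | 88.6% |
| 0.5 / 0.5 / 2.0 | 0.03% | 17.4% | 17.4% | 0.02% |
| 0 / 0 / 1.5 | 2.5% | 75.9% | 73.4% | 2.5% |
| 0 / 0 / 2.0 | 0.03% | 75.9% | 75.8% | 0.03% |

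A hand check on the last two rows: Week 24 almost never passes 1.0, since Φ((0.347 − 1.5)/0.333) = Φ(−3.46) = 0.03%. The clinical rule therefore comes down to both Weeks 4 and 12 passing. If visits were independent that would be 0.851² = 72.4%; correlation 0.5 raises it to 75.9%.

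**Range of the discordant probability.**
- Between-visit correlation 0 to 0.75: 70.6% to 76.0% for 0/0/1.5; 10.4% to 21.9% for 0.5/0.5/2.0; 1.2% down to 0.02% for no difference.
- Between-eye correlation 0.3 to 0.7 (SE 0.394 to 0.258), run with Week 24 at 3.0 mm Hg: 57.8% to 95.0%. At the plan's own 0.5 the 3.0 mm Hg case gives 75.9%, the same as 2.0.

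**The case against.** The strongest reply is that both documents introduce the rule as an addition. That can be read as a tighter tier on top of success: 1.5 at all three visits, and also 1.0 at two of them. The power statement cannot decide between the readings, because 88.9% (no condition) and 88.6% (conditional) both fit the stated 90%. This stands in part: a reader should not infer that the sponsor deliberately made the claim independent. But the condition is not written, while the corresponding condition for superiority is, and SAP Amendment 1.1 went back to clarify that one.

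Second, the clinical rule is not a formal test. The hypotheses in SAP 10.1 and Protocol 7.3.1 use 1.5 mm Hg only, the rule is not among the secondary analyses, and SAP 10.2.1 ties superiority to the statistical conclusion, so the clinical label opens no further test. This stands in full.

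Third, the plan hides nothing. All three differences and intervals are to be produced, so a failed Week 24 would be visible, and no text lets the clinical label replace the primary result. That limits the harm but does not remove the conflicting conclusion.

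Fourth, the large percentages depend on the assumed pattern. This also stands, which is why the 17% and 0.3% cases are shown with them. Nor is 76% an error rate for the rule as written: two visits truly are equal in that scenario, and the rule asks for two.

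**Conclusion.** The point holds as a gap in the decision rule. Followed as written, the plan can declare clinical noninferiority after its own 3-of-3 primary rule has failed. Under the plan's inputs this happens in about 73% to 76% of trials if Weeks 4 and 12 are truly equal and Week 24 is 1.5 to 2.0 mm Hg worse. It happens in 17% if the differences are 0.5, 0.5 and 2.0, and in 0.3% if there is no difference anywhere. These rest on assumed differences by visit and on a between-visit correlation of 0.5.

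Two stronger readings are not supported. A reader might infer that the trial's type I error is compromised; it is not, for either the primary or the superiority conclusion. A reader might also note that, with two visits exactly at 1.0 mm Hg and the third clearly better, the 2-of-3 rule passes 4.5% of the time (4.0% to 5.0% over visit correlation 0.75 to 0), above a one-sided 2.5%. But the plan never claims that level for this rule, and the gate would only lower the figure to 3.5%. That merits a note that the 2-of-3 step is supplementary and not controlled at 2.5%, not a finding of its own. The stated power figures are not in error.

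**What to change.** Before the primary database lock, state in SAP 10.1, Protocol 7.3.1 and the protocol summary: *Clinical noninferiority is concluded only if statistical noninferiority is first shown (upper limit at or below 1.5 mm Hg at all 3 visits) and the upper limit is at or below 1.0 mm Hg at at least 2 of the 3 visits.* A short note can add that the 2-of-3 step is a supplementary criterion not controlled at one-sided 2.5%.

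The cost is one sentence and about 0.3 percentage points of power for the clinical conclusion under no difference (88.9% to 88.6%). Sample size, data collection and the primary analysis do not change. In the assumed patterns with Week 24 at 1.5 or 2.0 mm Hg and no difference earlier, the chance of the clinical label falls from 75.9% to 2.5% and 0.03%. If the sponsor does mean the rule to stand alone, the text should say that it is descriptive and outside the error control.

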4.5.2 Prohibited Medications/Treatments

The decision to administer a prohibited medication/treatment is taken with the safety of the study participant as the primary consideration. When possible, Allergan should be notified before the prohibited medication/treatment is administered.

During the study, patients must not participate in other investigational drug or device studies.

Nonstudy IOP-lowering Treatments

Any concurrent nonstudy IOP-lowering treatment (eg, topical ophthalmic medication containing an ocular antihypertensive, LT) is prohibited in either eye during the study (through Month 24), unless necessary for the safety of the patient due to inadequate control of IOP as determined by the investigator. Inadequate control of IOP should be confirmed at a subsequent visit (scheduled or unscheduled visit). Initiation of treatment in one eye should not automatically lead to initiation of treatment in the contralateral eye. Each eye should be evaluated on an individual basis when determining the need for additional nonstudy IOP-lowering treatments. If nonstudy IOP-lowering treatment is initiated, the investigator will be expected to attest to the need for additional nonstudy IOP-lowering treatment for safety reasons for each eye individually. Use of any concurrent nonstudy IOP-lowering treatment with any known effect on study outcomes (eg, crossover effect on the contralateral eye) is prohibited during the study.

In order to maintain patient masking to treatments assigned to each eye, patients who have received nonstudy topical IOP-lowering treatment in a Bimatoprost SR eye will receive Sham Bimatoprost SR administration in that eye on the Bimatoprost SR Cycle 2 administration day(s). If nonstudy topical IOP-lowering medication is initiated in an SLT eye, the patient will continue to receive Sham Bimatoprost SR administration in the SLT eye on the administration day(s). In all cases, the contralateral eye that does not require nonstudy topical IOP-lowering medication will maintain the same treatment regimen assigned at randomization. Patients who have received nonstudy IOP-lowering treatment in both eyes will not receive Bimatoprost SR administration or Sham Bimatoprost SR administration in either eye, and therefore do not need to attend the Bimatoprost SR (or Sham Bimatoprost SR) administration visits and immediate postadministration visits (ie, Bimatoprost SR Cycle 2

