10.4.3 Treatment Effect Regardless of Non-Study IOP Treatment Use

To evaluate the treatment effect regardless of whether there is any use of non-study IOP lowering treatment, the MMRM analysis for primary analysis in Section 10.1 will be performed in the ITT population using all available Hour 0 IOP data. In this analysis, data after the use of non-study IOP lowering treatment will not be excluded.

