10.4.4 Tipping Point Analysis

A tipping-point analysis will be used to assess the robustness of the primary efficacy analysis with respect to possible deviations from missing at random (MAR) assumption in MMRM model. This analysis will evaluate the sensitivity of study results under the missing not at random (MNAR) assumption.

Tipping point analysis will be based on multiple imputed (MI) datasets for IOP data as described in Section 17.2 while applying a shift parameter to imputed IOP data for Bim SR 10 µg treated eyes. Specifically, missing IOP data will be calculated by adding a positive shift value to the imputed data to discount the treatment effect for Bim SR 10 µg. This shift will essentially make the IOP data higher than imputed for Bim SR 10 µg treated eyes. Note that there will be no shift applied to SLT treated eyes. With each shift, the MMRM analysis as specified for the primary efficacy will be performed based on the MI-based but shifted IOP data. SAS PROC MIANALYZE procedure will be used to aggregate the analysis results by using the parameter estimates from each imputed dataset.

Starting from a shift of 0 mmHg (ie, no shift), the above procedures will be repeated with incremental shift values of 1 mmHg. The shift values will be adjusted with unmasked data. The tipping point is reached when the analysis result being switched from positive (ie, Bim SR 10 µg is non-inferior to SLT) to negative (ie, Bim SR 10 µg is no longer non-inferior to SLT). The corresponding shift value is defined as the tipping point. If the IOP value at the tipping point is clinically implausible, the primary analysis results will be considered as robust.

The scientific plausibility, clinical relevance, as well as the interpretations of the different shift values will be discussed in the clinical study report.

10.4.5 Impact of Receiving the 2nd Bim SR After Week 16 and Prior to Week 24

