17.2.2 Multiple Imputation

Multiple imputation will be utilized to impute missing IOP values. The primary efficacy variable is Hour 0 IOP change from baseline assessed at Weeks 4, 12, and 24. However, to gain additional imputation efficiency, multiple imputation with a 2-step approach will be used for imputing missing IOP at Weeks 4, 8, 12, 15, 20, and 24 separately for each treatment group. The first step of multiple imputation will use the Markov Chain Monte Carlo (MCMC) method to impute intermittent missing data to achieve a monotone missing pattern. The second step will be based on a linear regression to impute the missing data. Note that baseline IOP values associated with each eye must not be missing in any of the patients; otherwise, they will be excluded from this analysis. Covariates to be included in the regression will be baseline Hour 0 IOP, race, sex, lens status, and age. The planned number of MIs is 25 and a prespecified seed of “123451” will be used for MCMC and a seed of “123457” for the regression part.

A sample code is shown below for Hour 0 IOP measurements associated with each eye:

```
proc mi data=iop nimpute=25 seed=123451 out=_miint;  
  var baseline week4_hr0 week8_hr0 week12_hr0 week15_hr0 week20_hr0 week24_hr0;  
  by treatment;  
  mcmc chain=single impute=monotone;  
run;  
  
proc mi data=_miint nimpute=1 seed=123457 out=mifull;  
  class race_group sex lens;  
  var race_group sex lens age baseline week4_hr0 week8_hr0 week12_hr0 week15_hr0 week20_hr0  
  week24_hr0;  
  monotone regression (week4= race_group sex lens age baseline/details);  
  monotone regression (week8= race_group sex lens age baseline week4/details);  
  monotone regression (week12= race_group sex lens age baseline week4 week8/details);  
  monotone regression (week15= race_group sex lens age baseline week4 week8 week12/details);  
  monotone regression (week20= race_group sex lens age baseline week4 week8 week12 week15/details);  
  monotone regression (week24= race_group sex lens age baseline week4 week8 week12 week15  
  week20/details);  
  by _imputation_treatment;  
run;
```

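### Should the primary MMRM also include the Week 15 and Week 20 IOP readings that probably trigger rescue before Week 24?

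*SAP*

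**What the plan says.** SAP 10.1 restricts the model to three visits ("avisitn = Derived analysis visits at Week 4, Week 12, and Week 24") and states that "IOP measurements obtained after initiating the use of non-study IOP-lowering medication or procedure in an eye will be treated as missing", which it identifies as the hypothetical strategy. Hour 0 IOP is also taken in both eyes at Weeks 8, 15 and 20 (Protocol Tables 3 and 4), but SAP 10.2.4 only summarises those values descriptively.

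Under Protocol 4.5.2 the investigator decides on nonstudy treatment for inadequate IOP control and should confirm it at a later visit, scheduled or not. The section adds: "Each eye should be evaluated on an individual basis when determining the need for additional nonstudy IOP-lowering treatments". Neither document gives a numeric rescue threshold or an expected rescue rate.

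Three further provisions bear on the point:

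- SAP 17.2.2: "multiple imputation with a 2-step approach will be used for imputing missing IOP at Weeks 4, 8, 12, 15, 20, and 24", separately by treatment. SAP 10.4.4 builds the tipping-point analysis on this imputation: "Starting from a shift of 0 mmHg (ie, no shift), the above procedures will be repeated with incremental shift values of 1 mmHg". Under SAP 10.1, multiple imputation is also the fallback if the MMRM does not converge.
- SAP 10.4.3 repeats the MMRM on all available readings: "data after the use of non-study IOP lowering treatment will not be excluded".
- Protocol 5.9.1.5 provides a second implant at Week 16 for a Bimatoprost SR eye with IOP above 17 mm Hg and none of the listed safety findings. Patients who reached Week 16 before Amendment 6 were retreated at a fixed Week 16. SLT eyes have no counterpart.

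**The concern.** An MMRM handles missing values validly if missingness depends only on data in the model. Between Weeks 12 and 24 the only scheduled IOP readings for all patients are those at Weeks 15 and 20. An eye rescued in that interval was therefore probably selected partly on readings the model never sees, so its missing Week 24 value is not missing at random given Weeks 4 and 12.

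If Bimatoprost SR were truly worse by the margin, and both eyes were judged by one threshold, more Bimatoprost SR eyes would be rescued. The model would then understate their Week 24 IOP and the noninferiority test would be slightly too lenient. Week 24 is one of three visits that must all pass, and the extra readings need no new data collection, so adding them looks like an easy gain.

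**Working it through.** **1. The plan's own figures.** SAP 15.0 gives SD 4 mm Hg and 144 patients, "assuming that both the between-eyes and the within-patient correlation coefficients are 0.5". SD of the paired difference = 4 × √(2 × (1 − 0.5)) = 4; SE = 4/√144 = 0.333. Power per visit is Φ(1.5/0.333 − 1.96) = 99.4% at margin 1.5 and Φ(1.0/0.333 − 1.96) = 85.1% at margin 1.0. With correlation 0.5 across visits, all three visits pass at 1.5 in about 98.3–98.5% of trials, and two of three at 1.0 in about 88.9%. The stated 98% and 90% are reproduced.

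**2. The bias without re-administration.** Assumptions not in the documents: 5% of SLT eyes rescued; one threshold for both eyes; rescue when IOP is high at Weeks 12 and 15, or at Weeks 15 and 20; between-visit correlation either constant at 0.5 or decaying as 0.4 + 0.6·exp(−weeks/8). The true difference is 1.5 at every visit. Negative values favour Bimatoprost SR.

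| | Constant | Decaying |
|---|---|---|
| Bimatoprost SR eyes rescued | 11.2% | 10.7% |
| Week 24 bias, three visits | −0.061 | −0.069 |
| Week 24 bias, six visits | 0.000 | 0.000 |

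One-sided error at Week 24 alone, nominally 2.5%:

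- constant: Φ(−1.96 + 0.0607/0.3341) = 3.8%
- decaying: Φ(−1.96 + 0.0691/0.3238) = 4.0%

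A second simulation with baseline IOP in the model, rescue above 26 mm Hg at scheduled readings from Week 12, and 160 patients gives −0.044 and −0.080 with three visits, and +0.007 and −0.003 once Weeks 15 and 20 are added. Over a wider set of rescue rules the three-visit bias is −0.02 to −0.10. With no true difference it is about zero.

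**3. Effect on the decision.** All three visits must pass. With a constant difference of 1.5, the joint error moves from 0.16% to 0.20% (constant correlation) or from 0.18% to 0.24% (decaying). Only if the difference is 0 through Week 12 and 1.5 from Week 15 does the Week 24 error carry through:

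- constant: Φ(−1.96 + 0.0544/0.3341) = 3.6%
- decaying: Φ(−1.96 + 0.0752/0.3238) = 4.2%

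**4. The same model with the Week 16 implant.** Step 2 treats Bimatoprost SR eyes as if no second implant existed. The true difference stays at 1.5; how rescue and retreatment interact is assumed.

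| Handling of high Bimatoprost SR eyes | Three visits | Six visits |
|---|---|---|
| Not rescued on the Week 15 reading (re-administered instead) | −0.10 to 0.00, median −0.02 | within 0.01 with Weeks 15 and 20 added |
| Half rescued, half not | −0.002 to +0.010 | not run |
| None rescued before Week 24 | +0.048 to +0.061 | not run |
| Retreated on Week 15 IOP, further drop of 1.5–2.5 mm Hg | about −0.06 to +0.11 | about +0.01 to +0.09 |
| Retreated, further drop of 2–3 mm Hg, none rescued | +0.077 to +0.130 | +0.038 to +0.068 |

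The first three rows give the second implant no effect on IOP; the last two do. There the six-visit model no longer comes out clean. A second implant triggered by Week 15 IOP changes how Week 15 relates to Weeks 20 and 24 in Bimatoprost SR eyes only, whereas the SAP covariance is indexed by primary or contralateral eye and so pools the two treatments.

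**5. Cost.** Unstructured covariance parameters: 6 × 7/2 = 21 now; 12 × 13/2 = 78 with six visits, 57 more. The Week 24 SE at 160 patients rises from 0.324–0.334 to 0.328–0.342. Single-visit power at margin 1.0 falls from Φ(1/0.334 − 1.96) = 84.9% to Φ(1/0.342 − 1.96) = 83.3%; with decaying correlation, from 87.0% to 86.0%.

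**The case for a change.** The best case for the change is one of principle. Missing at random given six visits is more credible than given three, the readings exist, and the SAP itself uses them for imputation. The noninferiority decision rests on the three-visit model, and no sensitivity analysis replaces it. Error in a noninferiority test is properly judged at the margin, where step 2 shows a lenient bias.

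The point about missing at random stands. Three parts of the argument do not.

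- **Direction.** One common threshold is an assumption. Protocol 4.5.2 asks only that eyes be judged individually, and the investigator who decides is unmasked (Protocol 9.4). A Bimatoprost SR eye that has received topical rescue gets sham in place of its second implant, so early rescue displaces study treatment in that eye alone. If high Bimatoprost SR eyes are rescued less readily, the bias vanishes or turns against Bimatoprost SR.
- **Remedy.** Near-complete removal holds only when scheduled readings drive rescue and the second implant does not alter the course of IOP. With an unscheduled confirmation one or two weeks later, six visits remove 66–82% of the bias; with both readings unscheduled, about 41%.
- **Consequence.** The one scenario that matters for the decision has the difference appear at about the time the second implant is due, with Week 24 eight weeks after it. Protocol 1.2.3 reports similar IOP lowering after the second administration. Late waning remains possible in eyes not retreated at Week 16, but that is a narrower case.

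The zero-shift step of the tipping-point analysis already conditions on all six visits and imputes within treatment, so it does not pool the two treatments when imputing. A simulated analogue was off by at most 0.03 mm Hg when scheduled readings drove rescue. The sample imputation code omits the fellow eye's IOP, a limitation in a secondary analysis.

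**Conclusion.** No change to the primary model is needed. Leaving out Weeks 15 and 20 does weaken the missing-at-random assumption, but the resulting Week 24 bias is probably about 0.1 mm Hg or less at moderate rescue rates when scheduled readings drive rescue. That is about 0.1/0.33 = 0.3 of a standard error. Its sign is not established: it favours Bimatoprost SR if one threshold governs both eyes and re-administration is ignored, and is near zero or against Bimatoprost SR if high eyes are retreated at Week 16 or rescued less often. Once retreatment has an effect on IOP, a six-visit model with the SAP's pooled covariance has bias of similar or larger size in many scenarios, and it brings the costs in step 5.

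All bias figures rest on assumed rescue rates, thresholds, between-visit correlations and retreatment effects, because the documents give none of these except the 0.5 correlation. The planned zero-shift imputation and the analysis that keeps post-rescue data already let a reader see whether the Week 24 result depends on this choice. Preferring six visits in the primary model is a matter of judgement, not a correction.
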